13.4.2.3 Overall Survival

Overall survival will be defined as the time in days from study entry until death. Patients who are alive on the date of closing follow-up will be censored on that date. All events of death will be included, regardless of whether the event occurred while the subject was still taking study drug, or after the subject discontinued study drug. If a subject has not died, then the data will be censored according to the following rule: if the subject was lost to follow-up, then data will be censored at the last study visit, or the last contact date, or the date the subject was last known to be alive, whichever is later; if the subject was not lost to follow-up, then data will be censored at the last study visit or the last contact date, whichever is later. The date of the last study visit will be determined by selecting the last available date of the following study procedures for a subject: tumor assessment, physical examination including neurologic assessment, vital signs assessment, blood chemistry and hematology collection, and performance status.

13.4.2.4 Time to Disease Progression

Time to disease progression will be defined as the time in days from study entry until progression or death. Patients who are free from progression on the date of closing follow-up or death will be censored on that date.

13.4.2.5 Duration of Disease Control

The duration of disease control for a given subject is defined as the number of days from the date the criteria are met for CR, PR, or SD (whichever is recorded first) to the date that recurrence or PD is objectively documented. The reference for PD will be the smallest measurements recorded since the treatment started. If a subject is still responding then the subject's data will be censored at the date of the subject's last study dose or last available tumor assessment, whichever is later. For subjects who never experienced CR, PR, or SD for 6 months, the subject's data will be censored on the date initiation of therapy.

13.4.2.6 Statistical survival analyses of marker levels to determine impact on prognosis and response to treatment

The relative risk for disease progression will be estimated using the Cox proportional hazards regression model. The Cox model will be used for both univariate and multivariate analyses provided the assumption of proportional hazards is verified. The Xtiles software(31, 32) will be employed to determine cut-points for the quantitative signals for analyzed biomarkers in association with survival and response to treatment as primary outcome. This software has built-in features for dividing the cohort into training and validation subsets, with correct assessments of p values for multiple cut-points. In the multivariate analyses of biomarkers, the Cox regression models will be adjusted for tumor size (continuous variable, 1 mm units), tumor grade (well, moderately, poorly differentiated), tumor stage (T1, T2, T3), lymph node metastasis (N0, N1). Univariable models will be run, with covariates having $p < 0.2$ included in backwards stepwise multivariable models. Final covariates will be retained with $p \leq 0.05$ based on two-sided tests. Limited interactions may be explored based on the final main effects model to avoid over-fitting of the models with this small sample size.

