8.5 Removal of Subjects from Therapy or Assessment

Each subject has the right to withdraw from study treatment at any time. In addition, the investigator may discontinue a subject from the study treatment at any time for any reason if the investigator considers it necessary, including the occurrence of an adverse event or noncompliance with the protocol. Each subject will be withdrawn from the study if any of the following occur:

- 1) The subject experiences either clinical or radiographic progressive disease.
- 2) The subject requires radiotherapy or alternate antineoplastic agents during the study period.
- 3) The investigator believes it is in the best interest of the subject.
- 4) Clinically significant deterioration of the subject's medical status as determined by the investigator.
- 5) The subject requires alternative anti-cancer agents or non-palliative radiation therapy for primary or metastatic disease during the treatment portion of the study.
- 6) Subject becomes pregnant or begins breastfeeding during the treatment portion of the study.
- 7) The subject or subject's legally acceptable representative decides to withdraw consent for any reason.
- 8) Any other medical reason that the study investigator deems appropriate.

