10.2.4.3 Progressive Disease (PD)

At least a 20% increase in the sum of the LD of target lesions, taking as reference the smallest sum LD recorded since the treatment started, the appearance of one or more new lesions and/or an unequivocal progression of non-target lesions.

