10.2.5 Definition of Disease Progression

Disease progression will be defined as:

- 1) Radiologic progression of disease by RECIST 1.1 criteria.
- 2) Clinical progression as determined by the investigator, which may be characterized as, but is not limited to:
 - a. Increase of at least 2 points in ECOG performance status attributable to cancer progression.
 - b. Requirement for palliative radiation, chemotherapy or surgery.
 - c. Death from disease progression.

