13.5.1.2.5 Duration of Disease Control

The distribution of the duration of disease control will be estimated using Kaplan-Meier methodology.

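### Duration of disease control counts only objectively documented PD as its event and gives no rule for death or unscanned clinical progression, which biases the estimate upward

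*Combined protocol and SAP*

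**What the plan says.** Section 13.4.2.5 starts the clock at the first CR, PR or SD and stops it "to the date that recurrence or PD is objectively documented". PD is defined in 10.2.4.3 by lesions: "At least a 20% increase in the sum of the LD of target lesions", new lesions, or unequivocal non-target progression.

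Two censoring rules follow in 13.4.2.5. A subject still responding is "censored at the date of the subject's last study dose or last available tumor assessment, whichever is later". The other rule reads: "For subjects who never experienced CR, PR, or SD for 6 months, the subject's data will be censored on the date initiation of therapy". Section 13.5.1.2.5 adds only the estimator: "The distribution of the duration of disease control will be estimated using Kaplan-Meier methodology".

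Elsewhere the protocol takes a wider view of progression. Section 10.2.5 adds a second limb, "Clinical progression as determined by the investigator, which may be characterized as, but is not limited to", and its examples include death from disease progression. Section 8.5 lists as a reason for withdrawal: "The subject experiences either clinical or radiographic progressive disease". PFS in 13.4.2.2 counts progression or death.

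One provision narrows the gap. Sections 8.5.1 and 10.1 call for a tumor assessment at the Final Visit, although 10.1 waives it if one was done within the previous four weeks.

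**The concern.** Patients with metastatic pancreatic cancer can lose disease control by clinical decline or death without a scan that shows PD. In this endpoint such a patient has no event, and neither censoring rule describes them: they are not still responding, and they did achieve control. If they are censored at the moment control is lost, the censoring is informative, because patients doing badly leave the risk set as though they might have stayed controlled. Duration of disease control is a named secondary endpoint of a single-arm trial, so no control arm carries the same bias to offset it.

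**Working it through.** **Step 1. How each ending is handled.**

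| How follow-up of control ends | Duration of disease control (13.4.2.5) | PFS (13.4.2.2) |
|---|---|---|
| PD on a restaging scan | Event | Event |
| Clinical progression, Final Visit scan shows PD | Event | Event |
| Clinical progression, no scan showing PD | No event, no rule | Event, using 10.2.5 |
| Death from disease, no PD scan | No event, no rule | Event |
| Death from another cause, no PD scan | No event, no rule | Event |
| Still in control | Censored at the later of last dose and last scan | Censored at close of follow-up |

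The third to fifth rows are the gap. The Final Visit scan moves some patients from the third row to the second. It cannot move all of them. A patient scanned as SD three weeks before clinical decline needs no new scan under 10.1. Section 8.5.1 says the Final Visit procedures must not hold up new treatment. A patient who dies on treatment has no Final Visit.

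**Step 2. Size if these endings are censored.** The plan states no expected value for this endpoint, so there is no figure to reproduce. The inputs are assumptions: a constant hazard λ for all losses of control, and a share q of losses without a PD scan, unrelated to time.

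- True median = ln 2 / λ.
- Counted hazard = (1 − q)λ, so estimated median = ln 2 / [(1 − q)λ].
- Ratio = 1/(1 − q): 1/0.85 = 1.18; 1/0.75 = 1.33; 1/0.60 = 1.67.

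For an assumed true median of 4 months, true control at 6 months is 0.5^(6/4) = 35%. The estimate becomes 0.5^(1.5(1 − q)): 41% at q = 15%, 46% at 25% and 54% at 40%.

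**Step 3. Allowing for scan timing and Final Visit imaging.** This is a simulation of 200,000 patients per setting. It assumes a 6-month median and uses scans every 8 weeks (4 cycles of 14 days, from 8.1). Here f is the share of endings that are clinical progression or death, before any Final Visit scan. The result is estimated control at 12 months; with all endings counted it is 0.27 to 0.28.

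| f | None shown as PD at Final Visit | Half shown | All shown |
|---|---|---|---|
| 10% | 0.31 | 0.30 | 0.28 |
| 20% | 0.35 | 0.31 | 0.27 |
| 30% | 0.40 | 0.33 | 0.27 |
| 40% | 0.45 | 0.35 | 0.27 |

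The bias shrinks as imaging captures more endings and vanishes only if it captures all of them.

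**Step 4. If these patients are dropped instead.** The factor 1/(1 − q) does not apply. With D endings, D-patients' person-time P and person-time C from patients censored in control, the true rate is D/(P + C). Dropping the share q gives (1 − q)D/[(1 − q)P + C], which is lower whenever C > 0. The direction is again upward, by an amount that depends on C.

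**Step 5. The later-of rule.** Dosing continues between scans, which are 8 weeks apart, or up to 12 weeks with delays. The last dose can therefore fall weeks after the last scan, and that unassessed time is credited as control. The rule covers only subjects still responding, and its effect was not quantified.

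**The case against.** The strongest reply is that an objective-PD endpoint is a legitimate quantity, reported beside PFS and OS, and that differing from PFS is not in itself an error. Investigator-judged clinical progression, with an open-ended list in 10.2.5, is also a soft event in an open-label trial. Both points stand. They are why clinical progression belongs in a sensitivity analysis and not in the main definition. They do not justify leaving out death, nor leaving these patients without a rule.

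A reader might infer that clinical progression can never count. The documents do not support that: the Final Visit scan can show PD, and then it counts. A reader might also infer that the plan orders these patients to be censored as controlled. It does not; it is silent, and censoring or dropping is what remains under Kaplan-Meier. An analyst might fill the gap from 10.2.5, but 13.4.2.5 asks for objective documentation and does not refer to that section.

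It is also fair that q and the medians are not in the documents, and that the ORR decision rule in 13.2 and 13.3 is untouched.

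**Conclusion.** The point holds. As written, the endpoint omits death as an event, omits clinical progression unless a scan shows PD, and leaves the patients affected without a rule. The bias is upward whenever some control ends without objective PD and those patients are censored. Its size is unknown. The factors 1.18, 1.33 and 1.67 illustrate assumed shares of 15%, 25% and 40% under a constant hazard and do not predict what this trial will show. Reading them as a demonstrated inflation would go beyond the documents, because Final Visit imaging could make the remaining share small. The later-of censoring rule adds a separate upward push for subjects still responding. The consequence is confined to this secondary endpoint.

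**What to change.** In 13.4.2.5:

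- For subjects who achieved disease control, define the event as the first of objectively documented PD or recurrence, or death from any cause.
- Censor controlled subjects without an event at the last adequate tumor assessment, and delete the last-dose alternative and the later-of clause.
- Add a sensitivity analysis that also counts clinical progression per 10.2.5 as an event.
- Reconcile the last sentence, which censors subjects without control at the start of therapy, with this wording. Otherwise the section would mix a definition limited to controlled subjects with a rule for those who never entered it.

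The cost is a few sentences of analysis text and one extra analysis. No additional visits or scans are needed. The reported duration may be shorter.

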2.4.2 Secondary Objectives

2.4.2.1 Secondary Clinical Objectives: To determine, in patients with metastatic pancreatic cancer treated with ABT-888 combined with 5FU and oxaliplatin:

- 1) Disease control rate (CR+PR+SD at 6 months)
- 2) Progression free survival
- 3) Overall survival
- 4) Time to disease progression
- 5) Duration of disease control
- 6) Tolerability and safety of the combination
- 7) Degree of Neuropathy, as measured by the FACT/GOG-NTX-4 (Version 4)

2.4.2.2 Secondary Scientific Objectives To correlate the response rate of ABT-888 plus 5FU and oxaliplatin to:

- 1) Tumors that have decreased expression of or mutations in BRCA-1 or -2 or related pathway genes.
- 2) PARP activity levels in serial tumor samples
- 3) Expression levels of DNA repair enzymes in tumor tissues
- 4) Pharmacokinetic and pharmacogenomic parameters associated with the metabolism of ABT-888
- 5) To isolate and propagate tumor cell lines obtained from patient samples and circulating tumor cells

2.5 Trial Design Summary:

This is a single arm, open-label Phase I/II study to evaluate the clinical activity of the combination of the novel inhibitor of Poly(ADP-ribose) polymerase (PARP), ABT-888 combined with 5FU and oxaliplatin in patients with metastatic pancreatic cancer. Patients with metastatic, unresectable pancreatic cancer, and with a known BRCA-associate genetic mutation OR family history suggestive of a breast or ovarian cancer syndrome (as defined in the inclusion criteria) who still have an adequate performance status and normal hepatic and renal function will be eligible. Patients will be stratified into two groups: Untreated or previously treated:

- Untreated patients should have received zero prior therapies for metastatic disease.
 - i. They may have received prior adjuvant chemotherapy and/or radiation therapy, but not within 6 months prior to treatment.
 - ii. They may have received prior *palliative* radiation therapy for unresectable disease, but without any systemic chemotherapy, even as a radiosensitizer
- Previously treated patients may have received any number of prior therapies, including prior adjuvant chemotherapy and/or radiation therapy within 6 months of treatment.

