10.0 EFFICACY ASSESSMENT

10.1 Efficacy Variables

Tumor response and/or disease progression will be assessed by CT scan, MRI, CT/PET scan, X-ray, or ultrasound utilizing RECIST 1.1 criteria. The imaging modality will be at the discretion of the investigator BUT must be consistent from screening to reassessment for each patient (e.g. CT at baseline \rightarrow CT at reassessment). Assessments will be performed at Screening, and every 4 cycles thereafter (or not more than every 12 weeks if there have been treatment delays), and at the Final Visit, if not performed within the last four weeks. If subjects respond to treatment and are able to have their disease resected, the patient's response will be assessed prior to the surgery.

The *clinical* efficacy endpoints will be the objective response rate (ORR), as determined by RECIST criteria. Secondary clinical endpoints are listed above, and include disease control rate (DCR, defined as response rate + rate of stable disease at 6 months), progression free survival (PFS), overall survival (OS), time to disease progression (TTP), duration of disease control (DDC), and tolerability and safety of the combination. Analyses of these endpoints are described in Section 13.

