10.2.4.4 Stable Disease (SD)

Neither sufficient shrinkage to qualify for PR nor sufficient increase to qualify for PD, taking as reference the smallest sum LD since the treatment started.

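### Duration of disease control drops observed early progressions by censoring them at day 0, and the disease control rate has two definitions

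*Combined protocol and SAP*

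**What the plan says.** **Duration of disease control.** Section 13.4.2.5 runs the clock "from the date the criteria are met for CR, PR, or SD (whichever is recorded first" until recurrence or PD is objectively documented, with no minimum length of control. Patients still in control are censored at the "last study dose or last available tumor assessment, whichever is later". The final sentence concerns a further group: "For subjects who never experienced CR, PR, or SD for 6 months", for whom the "data will be censored on the date initiation of therapy". Section 13.5.1.2.5 adds: "The distribution of the duration of disease control will be estimated using Kaplan-Meier methodology". Section 13.5 applies the efficacy analyses to all subjects, apart from those planned only for a subgroup.

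**Disease control rate.** Section 2.4.2.1 gives the objective as "Disease control rate (CR+PR+SD at 6 months", and 7.2.1 repeats it. Sections 2.5 and 8.1 define DCR as ORR plus stable disease at 6 months. Section 10.1 has "disease control rate (DCR, defined as response rate + rate of stable disease at 6 months" and refers to Section 13 for the analysis. In Section 13 the time condition is absent. Section 13.4.2.1 asks for a confirmed SD, PR or CR and points back to section 10. Section 13.5.1.2.1 reports the proportion achieving SD, PR or CR. The SD definition in 10.2.4.4, "Neither sufficient shrinkage to qualify for PR nor sufficient increase to qualify for PD", sets no minimum duration.

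**The concern.** The first and last sentences of 13.4.2.5 conflict. A patient with SD at week 8 and PD at week 16 has an observed duration of 56 days under the first, and is censored before the clock starts under the last. Kaplan-Meier estimation needs censoring to be unrelated to outcome; here, failing early is what triggers it. The text leaves open whether the 6 months qualifies SD alone or CR, PR and SD together, but progressions are lost either way: those of early-progressing SD patients under the first reading, and those of early-progressing responders as well under the second.

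At stake is a named secondary endpoint that would overstate how long control lasts, in a single-arm trial where no comparator shares the bias. For DCR, two analysts following the same document could report materially different rates.

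**Working it through.** The plan states no DDC or DCR figure, so there is none to reproduce. The direction of the bias follows from the estimator; its size needs assumptions.

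**Step 1: effect of day-0 censoring.** Kaplan-Meier multiplies terms (1 − d/n) over event times t > 0, where n counts patients whose time is at least t. A patient censored at or before time 0 is in no n and no d. The rule therefore has the same numerical effect as deleting the patient.

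**Step 2: hypothetical stratum of 24.** Eight patients progress at the first scan and have no DDC. Sixteen have control lasting 8 (×5), 16 (×3), 24 (×3), 32 (×2), 40 (×2) and 48 (×1) weeks.

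- All events counted: control beyond 16 weeks is 8/16 = 50%; median 16 weeks.
- 6 months qualifies SD only (6 of the 8 short durations are SD): 10 patients remain, control beyond 16 weeks is 8/10 = 80%; median 24 weeks.
- 6 months qualifies all categories: 8 patients remain, control beyond 16 weeks is 8/8 = 100% by construction; median 32 weeks.
- DCR: 16/24 = 67% with any SD (exact 95% CI 45% to 84%). It is 10/24 = 42% (22% to 63%) if six of those had SD ending before 6 months.

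**Step 3: expected size.** From the plan: 14-day cycles with restaging every 4 cycles, so scans every 8 weeks (8.1), and 24 patients per stratum (13.3). Assumed: exponential time to progression; PD documented at the next scan; the week-24 scan taken as 6 months; responders 0% to 25% of all patients, drawn at random from those controlled at week 8; no other censoring.

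Let q be the probability of being progression-free over 8 weeks (56/30.4375 = 1.84 months). For a median of 4 months, q = 2^(−1.84/4) = 0.727, q² = 0.529 and q³ = 0.384.

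- DCR with any SD: q = 0.727.
- DCR under the objective: with no responders, q³ = 0.384. With 25% responders, 0.25 + (0.727 − 0.25) × 0.529 = 0.502.
- DCR if SD must be confirmed at week 16: q² = 0.529 to 0.25 + 0.477 × 0.727 = 0.597.
- Progressions lost: all categories, 0.727 − 0.384 = 0.343. SD only with 25% responders, 0.727 − 0.502 = 0.225. Of 24 patients that is about 8 and 5.
- Control beyond 16 weeks from first documentation: all events counted, q² = 53%. SD only, 0.384/0.502 = 77%. All categories, 100%.
- Median DDC: all events counted, 24 weeks, because the curve falls from q² = 0.529 to q³ = 0.384 there. SD only with 25% responders, 32 weeks. All categories, 40 weeks.

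| | Median 4 months | Median 6 months |
|---|---|---|
| DCR, any SD | 73% | 81% |
| DCR, SD confirmed at week 16 | 53–60% | 65–70% |
| DCR, objective | 38–50% | 53–62% |
| Patients whose PD is lost | 22–34% | 19–28% |
| Median DDC, all PD counted | 5.5 months | 7.4 months |
| Median DDC, SD-only reading (25% responders) | 7.4 months | 9.2 months |
| Median DDC, all-categories reading | 9.2 months | 11.0 months |
| 16-week control: all PD counted / SD only (25% responders) / all categories | 53 / 77 / 100% | 65 / 86 / 100% |

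Simulation of 400,000 patients agrees with the closed forms. In 20,000 simulated strata of 24 with up to 6 responders, the written rule gave a longer median DDC in 84% (SD only) or 94% to 95% (all categories).

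**Step 4: sensitivity.** Over medians of 3 to 8 months and 5% to 25% responders, the written rule lengthens median DDC by 8 to 16 weeks. At a median of 8 months, the lost progressions fall to 16% to 23% of patients. If 6 months means the week-32 scan, then at a median of 4 months they rise to about 29% to 45%, and DCR under the objective falls to 28% to 43%.

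**The case against.** The best counter-argument is that the last sentence of 13.4.2.5 is a clumsy exclusion: since the protocol's disease control means SD at 6 months, DDC may be meant only for patients who met that criterion. That estimand is legitimate, but the text does not deliver it. The clock still starts at the first SD, so SD patients carry a guaranteed event-free period. It would need a 6-month landmark with the clock started there.

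On DCR, 13.5.1.2.1 can be read as a reporting sentence that inherits a definition given five times elsewhere. That is fair as a guess at intent, and so the loss of favourability in the reported DCR is possible rather than certain. But 10.1 sends the reader to Section 13, where the condition is missing. The pointer from 13.4.2.1 to section 10 reaches both the 6-month DCR (10.1) and an SD definition with no duration (10.2.4.4), and the word confirmed adds a third possible reading.

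Three limits stand. The sizes are illustrative, because the documents give no progression-free survival for this regimen in the selected population. Section 10.2.5 allows clinical progression while 13.4.2.5 needs objective documentation, so the share of lost events is towards the upper end for the week-24 choice. And under the SD-only reading with 25% responders, patients selected for lasting 6 months are only about half of the curve at a median of 4 months (0.252/0.502), and 41% at 3 months. Patients with PD as best response have no duration of control; leaving them out is correct.

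**Conclusion.** The concern holds on both parts. As written, the DDC rule removes patients who had control and then an observed progression, and the resulting curve is too high under either reading of the 6-month phrase. That direction does not depend on a model. Under the stated assumptions with medians of 4 to 6 months, about a fifth to a third of patients lose an observed progression and median DDC is overstated by roughly 2 to 4 months. DCR differs between its two definitions by 19 to 34 percentage points (81 − 62 to 73 − 38, rounded). A smaller point, not quantified, is that ongoing control may be censored at a dose given after the last scan. The consequence is confined to secondary, descriptive endpoints: the ORR decision rule is unaffected, and progression-free survival (13.4.2.2) still counts every early progression. The wording should be corrected.

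**What to change.** **13.4.2.1 and 13.5.1.2.1.** Use the objectives' definition in both: CR or PR, or SD still present at 6 months from study entry. Name the scan that counts as 6 months, since the 8-weekly scans fall at weeks 24 and 32.

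**13.4.2.5.**
- Delete the day-0 censoring sentence.
- Define the DDC population as all patients with any documented CR, PR or SD, however short, and say that it is deliberately wider than the DCR numerator. Patients with none of these are not in the analysis.
- Count every documented PD as an event on its date.
- Censor ongoing control at the last adequate tumour assessment, not at a later dose.
- State how death without documented PD is handled, for example as an event, as progression-free survival does.

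If the team wants DDC only among patients with 6-month control, a stated 6-month landmark with the clock started there is a workable alternative.

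The cost is wording only; no new data are needed. Reported DDC will be less favourable, and so will DCR if any SD would otherwise have been counted.

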13.2 Study Design

The dose of ABT-888 will be determined by a brief Phase I dose escalation study. A traditional 3+3 dose escalation approach with doses of ABT-888 ranging from 40mg to 300mg will be employed to determine the recommended Phase II dose of 5FU and oxaliplatin plus ABT-888. It is possible, even likely that the Phase I portion of this study will identify the RP2D of ABT-888 as 40mg, thus as few as 9 patients may be enrolled in the Phase I portion of the study.

This trial will follow a standard 3+3 Phase I design. Patients are enrolled in groups of three. The following dose escalation rules will be used and applied to Cycle 1 of therapy:

- 1) Three patients are studied at the first dose level.
- 2) If none of these three patients experience DLT, then the dose is escalated to the next higher level in the three subsequent patients.
- 3) If one of three patients experiences DLT at the current dose, then up to three more patients are accrued at the same level.
 - a) If none of these three additional patients experience DLT, then the dose is escalated in subsequent patients.
 - b) If one or more of these three additional patients experiences DLT, then patient entry at that dose level is stopped, the MTD has been exceeded and dose escalation will be stopped. Up to three more patients are treated at the next lower dose (unless six patients have already been treated at that prior dose).
- 4) If two or more of a cohort of up to six patients experience DLT at a given dose level, then the MTD has been exceeded and dose escalation will be stopped. Up to three more patients are treated at the next lower dose (unless six patients have already been treated at that prior dose).
- 5) Using this dose escalation scheme, the probability of escalating to the next dose level, based on the true rate of DLT at the current dose, is given by the following table:

True DLT rate at a Given Dose						
	10%	20%	30%	40%	50%	60%
Probability of Escalating	.91	.71	.49	.31	.17	.08

Thus, if the true underlying proportion of toxic events is 30% at the current dose, there is a 49% chance of escalating to the next dose.

The phase II portion of the trial will follow two parallel Simon's two-stage optimal designs(1) that will continue or stop independently from one another. For each stratum, in the first stage, 9 patients will be accrued. If none

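### The biomarker Cox plan in 13.4.2.6 sets no marker list and no error control across markers, selects terms stepwise, and leaves the prior-therapy stratum out of its adjusters

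*Combined protocol and SAP*

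**What the plan says.** Section 13.4.2.6 describes Cox models for disease progression with biomarkers as predictors.

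- **Cut-points.** X-tile software "will be employed to determine cut-points for the quantitative signals for analyzed biomarkers in association with survival and response to treatment as primary outcome".
- **Software safeguard.** The next sentence says: "This software has built-in features for dividing the cohort into training and validation subsets, with correct assessments of p values for multiple cut-points".
- **Adjusters.** Size (as a continuous measure) and grade (three levels) are listed for the multivariate models, together with "tumor stage (T1, T2, T3), lymph node metastasis (N0, N1"). Prior-therapy group is not listed.
- **Selection.** "Univariable models will be run, with covariates having $p < 0.2$ included in backwards stepwise multivariable models". Terms stay at p≤0.05 "based on two-sided tests". Over-fitting in a small sample is acknowledged, but only as a reason to limit interactions.

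The section gives no number of markers, analysis set, number of events or correction across markers, and does not call the results exploratory. Elsewhere:

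- The design is split by prior therapy. Section 13.2 describes "two parallel Simon's two-stage optimal designs" that continue or stop independently, and 13.1 states the Phase II primary objective by prior-therapy stratum.
- Table 7 (12.3.4) lists the DNA-repair panel and allows genes to be added. Section 12.3.6 sends to quantitative staining those markers that emerge from the panel.
- Sections 13.5.2.2 and 13.5.2.3 label the PARP-activity and DNA-repair response comparisons as pilot and hypothesis-generating, with 10 patients each.

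**The concern.** Three features combine. Cut-points are tuned to outcome, terms are chosen by their p-values, and an unspecified number of markers is each judged at 0.05. The p-values and hazard ratios that survive will then look stronger than the data warrant, by an amount nobody can calculate afterwards because the number of tests was never fixed.

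Separately, untreated and previously treated patients may well differ in prognosis. If marker levels also differ by prior therapy, a model that ignores the stratum credits the marker with part of that difference.

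The go/no-go decision rests on response rate and is untouched. At stake is which markers are carried forward as predictors of benefit, an objective the protocol lists by name (7.2.2).

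**Working it through.** **1. Sample size.** The plan gives no figure for this analysis; the nearest is the Simon design behind 24 per stratum (13.3). The probability of a positive result is

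Σ over x = 1 to 9 of C(9,x) pˣ(1−p)⁹⁻ˣ · P[Bin(15,p) ≥ 3−x].

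This gives 0.093 at p = 0.05 and 0.903 at p = 0.25, so the stated 10% and 90% are reproduced. Two full strata make 2×24 = 48 patients. If a stratum stops at 9, the total is 9+24 = 33 or 9+9 = 18. Other counts in the document are 50 specimens (12.3.5), 24+48 subjects (8.1) and 10 patients (13.5.2.3). I use 48.

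**2. Parameters.** Size takes 1 degree of freedom, grade 2, T stage 2 and N 1, so 6; one marker makes 7. Even if all 48 patients have events, that is 48/7 = 6.9 events per parameter. With 10 patients it is at most 10/7 = 1.4.

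**3. Cut-point search, one null marker.** Simulation with exponential times, 10% censoring and the log-rank test at 0.05. The ranges reflect trimming of 20% or 10% at each end of the marker.

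| Patients | Searched cut, uncorrected | Cut chosen in one half, tested in the other | Fixed median split |
|---|---|---|---|
| 24 | 32–41% | 8–9% | 7% |
| 48 | 30–43% | 7% | 6% |
| 72 | 30–44% | 6–7% | 6% |

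Held-out validation almost removes the problem. An uncorrected search multiplies the error six- to nine-fold, and more patients do not help.

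**4. Several markers.** The number k is not stated, so a range is needed. My count of distinct gene names in Table 7 is 82. For k independent null markers at a valid 0.05 each, P(at least one false) = 1 − 0.95ᵏ. The other two columns simulate the full rule at 48 patients: p<0.2 screen, backward selection to 0.05, with six null adjuster terms.

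| k | 1 − 0.95ᵏ | Full rule, continuous markers | Full rule, uncorrected cuts |
|---|---|---|---|
| 1 | 5% | 5% | 46% |
| 5 | 23% | 26% | 93% |
| 10 | 40% | 48% | about 100% |
| 20 | 64% | 76% | about 100% |
| 82 | 98.5% | not run | not run |

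The formula passes 95% only at k = 59. These runs used 400 (continuous) and 200 (cut) replicates, so each figure carries up to about ±5 or ±7 points.

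**5. Omitted stratum.** The documents give neither the prognostic gap nor any marker difference between strata, so both are assumed: a between-stratum hazard ratio of 2 to 2.5 and a marker shift of 0.5 to 1 SD, with no true marker effect. One set of simulations gave about 9–23% false positives unstratified against about 5% stratified. A second set, with 24 patients per stratum, 10% censoring and 3,000 runs per setting, gave:

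| Hazard ratio | Shift (SD) | Unstratified | Stratified |
|---|---|---|---|
| 2 | 0 | 5% | 6% |
| 2 | 0.5 | 7% | 5% |
| 2 | 1 | 15% | 5% |
| 2.5 | 0 | 6% | 6% |
| 2.5 | 0.5 | 9% | 5% |
| 2.5 | 1 | 21% | 5% |

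Without a shift there is no inflation.

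**The case against.** A reader might infer that this plan will almost surely report false markers. The documents do not support that.

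- **The cut-points have a stated safeguard.** The sentence on training and validation subsets directly follows the one on cut-points. If it is followed, the per-marker rate is about 7%, and the 30–43% does not arise. This stands. But the sentence describes what the software can do. It does not say which p-value will be reported or carry the correction into the later Cox models, and it covers several cuts of one marker, not several markers.
- **The number of markers is unknown.** Table 7 is a screening panel, and 12.3.6 suggests that only a subset reaches quantitative staining. Near-certainty needs roughly 59 or more independent markers, or uncorrected cuts. This stands too. If the subset is chosen from the same patients by looking at outcome, however, counting only the final markers understates the multiplicity; the rule is not given.
- **The p<0.2 rule may not apply to markers.** It speaks of covariates straight after the adjusters are listed, so it may govern only size, grade, T and N. The text leaves this open, as it does whether the adjusters are forced in. The 1 − 0.95ᵏ column applies under either reading.
- **Omitting the stratum does not by itself create false markers.** Correct, and the section does not say outright that strata are pooled; but it provides no stratum term.

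A reader might also infer that T and N cannot be adjusted for because every patient is metastatic and 8.3.2.3 does not list them. That list is not exhaustive, and 12.3.1 expects resection blocks, so unavailability is not shown.

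**Conclusion.** The concern holds as a gap in specification and error control. The plan fixes no marker list, controls no error across markers, leaves the scope of its selection rule unclear, does not commit to validated cut-points in the Cox step, omits the stratum, and lacks the exploratory label given to its sister analyses.

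If cut-points are validated or markers stay continuous, the size is set mainly by the number of markers: modest for one, roughly a coin toss for 10, close to certain only for the whole panel. The family-wise figures rest on independent null markers, and the simulations on 48 patients and 10% censoring; correlated repair genes would lower the family-wise rates. The stratum bias is conditional on an assumed marker difference between strata, but it is avoidable at no cost in data. I rate this as a change that should be made, not one that threatens the trial's primary conclusion.

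**What to change.** Rewrite 13.4.2.6 as follows:

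1. Stratify every biomarker Cox model by prior therapy (untreated or previously treated).
2. Name the markers and the analysis set before outcomes are examined, and reconcile the 48, 50, 24+48 and 10.
3. Drop the p<0.2 screen and backward selection. Test the listed markers one at a time, as continuous values; for any cut-point, report only the validated, search-corrected p-value.
4. Report hazard ratios with 95% confidence intervals and FDR-adjusted p-values across all markers tested, including any used to choose which markers go forward.
5. Label the section exploratory, in line with 13.5.2.2 and 13.5.2.3.

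Adding ECOG status is optional. T and N need go only if they are not recorded.

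The change is to wording; the stratum is already recorded. The price is fewer nominally significant markers and no ready-made cut-point. For a true hazard ratio of 2 with a 50/50 split and 48 events, power is Φ(ln 2·√48/2 − 1.96) = Φ(2.40 − 1.96) = 67% at 0.05. It falls to 34% at 0.05/10 = 0.005, the Bonferroni level for 10 markers and a stricter standard than FDR. That is a reason to keep the list short.
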